Development of a Behavioral Intervention for Chronic Pain in Individuals With HIV
NCT02824562

STUDY PROTOCOL

Version 1.0
Sep, 2017

Send Questions or Comments to:
[name] [contact]
[name] [contact]

I. STUDY OVERVIEW

Defined as pain lasting longer than three months, chronic pain affects up to 30% of the US population. It often occurs in patients with complex chronic illness, including medical, psychiatric, and substance use comorbidities. However, chronic pain is not simply a symptom of these comorbidities. Its distinct neurobiologic basis and substantial impact on physical and emotional function make it a serious illness in itself. In recognition of its importance, the Institute of Medicine has called chronic pain a “public health crisis,” and identified research on chronic pain, particularly in populations most burdened by this condition, to be a priority.

The burden of chronic pain in HIV-infected patients is substantial. Prevalence estimates of chronic pain in HIV-infected patients are as high as 39-85%. Mounting evidence suggests that chronic pain in HIV is often associated with psychiatric illness, especially mood disorders such as depression, and has serious health consequences, including up to 10 times greater odds of functional impairment.

Non-pharmacologic, behavioral interventions to decrease pain and improve physical and emotional function in HIV-infected patients with chronic pain are needed. A consensus panel identified pain, physical, and emotional function to be the most important outcomes of chronic pain interventions. Commonly used pharmacologic therapies, including opioids, often do not result in substantial improvement in these outcomes, and carry risks including misuse, abuse, and addiction. In HIV, opioids may

actually be associated with worse pain, and adversely interact with antiretrovirals. Behavioral interventions are among the most effective and safe non-pharmacologic treatments for chronic pain in the general medical population.

II. OBJECTIVES

In this study we will conduct a two-arm pilot randomized controlled trial of the chronic pain behavioral intervention to investigate feasibility, acceptability, and when possible, preliminary impact.

III. STUDY ACTIVITIES

a) STUDY POPULATION

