A total of 40 patients (up to 60) who are patients at the UAB 1917 clinic, enrolled in CNICS, experiencing chronic pain (Brief Chronic Pain Screening Questionnaire (BCPQ) = at least moderate pain for at least 3 months) and moderately severe and impairing chronic pain (PEG pain questionnaire = average of all three times is 4 or greater).

Inclusion Criteria

1. Enrolled in CNICS
2. Age \geq 18 years
3. Chronic pain (Brief Chronic Pain Screening Questionnaire (BCPQ) = at least moderate pain for at least 3 months)
4. Moderately severe and impairing chronic pain (PEG pain questionnaire = average of all three times is 4 or greater)

Exclusion Criteria

1. Do not speak or understand English
2. Are planning a new pain treatment like surgery

3. Cannot attend the group sessions

Recruitment of participants will take place in the 1917 clinic. Participants will be recruited via word-of-mouth by clinic staff or providers, calls generated from flyer tear-offs, and responses to the flyer on the TV monitors.

b) PRE-SCREENING

Potential participants will be prescreened over the phone using our prescreening phone script. If the individual passes the telephone prescreen, he or she will be scheduled for an in-person pre-screening visit by a member of the STOMP recruitment team. The date and time of the pre-screening visit along with the participant contact information and preferred method of contact will be recorded on the Prescreening Visit Appointment Form. About 48 hours prior to the in-person prescreen visit, a reminder call from the research staff will be made to remind the potential participant of the prescreening visit. On the day of the prescreen, the research staff member conducting the prescreen will log onto Redcap and establish a unique RedCap instance for this participant and complete the prescreen section only. At the end of the prescreen, the research tech will record the participant's eligibility on the Prescreening Visit Appointment Form. If the participant is eligible for enrollment, a Screening and Enrollment Visit will be scheduled and recorded on a Screening and Enrollment Visit form. The participant will also be thanked and given their \$25 incentive.

If the participant is not eligible, he or she will be thanked for their time and give their \$25 incentive.

c) SCREENING AND ENROLLMENT

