The Screening and Enrollment Visit will be scheduled approximately 2-4 weeks from the date of the pre-screen visit and recorded on a Screening and Enrollment Visit form. Participants will receive a reminder call at about a week and 48 hours prior to the scheduled screening visit. At the beginning of the screening and enrollment visit, the participant will complete the informed consent process.

Informed Consent Procedures

Informed consent will be administered by staff trained in accordance to the University of Alabama at Birmingham Institutional Review Boards guidelines for obtaining informed consent. The staff member obtaining consent must verify the following: protocol name, version number, dates for use, and institution. The Study team member will also ensure that the most recent informed consent is being used for the study. Initial informed consent must be completed and documented before any other study related procedures are done.

Comprehension will be assessed by asking the participant to summarize the study activities or some general open ended questions will be asked like what can you tell me about this study, can you tell me about how long the study may last, etc.

The consent process is estimated to take around 30 minutes.

Study staff will ensure that the participant has signed and dated the consent form including the HIPAA form.

All signed consent forms will be stored in locked file cabinets under respective participant files.

Baseline Assessment

The research staff will then administer the baseline assessment which includes a confirmatory set of screening questions via RedCap. Confirmation of the participant's eligibility will be recorded in RedCap.

Following completion of the baseline assessment, participants will be thanked for coming and given their \$50 incentive payment for their time. Completion of Baseline assessment will be recorded in excel logs.

d) RANDOMIZATION

Our team will utilize a 1:1 ratio for allocation to the treatment and control arms at each participating site. The UAB statistician will generate a list of random arm assignments for each site. Randomization list will be provided to the study coordinator to create sealed envelopes with participant ids on it in chronological order.

Once the participant completes the enrollment procedures, study staff will open the sealed envelope and will show the random arm assignment to participant and record it in the excel logs.

e) ASSIGNMENT OF ARM OF STUDY

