Approximately, 20 intervention arm and 20 control (standard of care) participants will be randomly assigned. Recruiting staff and research personnel will be masked to treatment arm assignment at the initial study visit. After the initial study visit, study coordinator will inform the participant of the follow-up assessments and thank the participant for their time. Staff personnel doing the assessment will still be blinded to the arm assignment.

If the participant is randomized to the intervention group, the participant will be informed of the next steps which includes the first group session. If the date of the first group

session has been established, the participant will be informed of the date and time. If it has not been scheduled, the participant will be informed that s/he will receive a call within the next two weeks informing his/her with the date and the time of the first group session

f) INTERVENTION

This behavioral intervention consists of 12 intervention sessions (6 group and 6 individual sessions). The sessions will be completed over a period of 12-16 weeks from enrollment. The first intervention session will be a group session for all participants followed by individual and then alternating group and individual session for the rest of the sessions.

Group intervention Sessions

A total of 6 group sessions will be conducted over a period of 12-16 weeks from study enrollment date. These sessions will be led by a peer. A peer is an HIV-infected patient of the UAB 1917 Clinic living with chronic pain, who has completed all ten of the one-on-one sessions offered, received training to co-facilitate the six group sessions with the interventionist, and is successfully self-managing his/her chronic pain.

Participants will receive a reminder call/text approximately 48 hours before the group session to remind them of the upcoming session. Participants will also be notified of the upcoming group sessions at the end of each one-on-one intervention. Group sessions will be conducted in UAB 1917 clinic building or the Bevill Biomedical Research Building (BBRB). A sign-in sheet will be used to document attendance. Session notes will be used to document any major issues presented or any anecdotal nuances identified. The date, start time and end time of the session will also be documented. Participants will

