complete an anonymous session feedback form at the end of each session. Each session will be audio recorded and transcribed later using a third party.

Individual Intervention Sessions

A total of 6 individual sessions will be conducted over a period of 12-16 weeks from study enrollment date.

Each individual intervention session will be scheduled by the staff interventions preferably prior to next group session. The intervention date and time will be recorded on the Individual Intervention Session Form along with the intervention no. and topic. The participant will receive a reminder communication about the upcoming session approximately 48 hours before the session. An Intervention Session Form will be used to record the date, time, length of session, topic covered, homework, next steps, and any nuances identified during the session. An adverse event form will be completed if any physical, social or psychological issues arise a result of participating in this study and warrant immediate attention. The date of the next group session will be announced and the date of the next one-on-one session will be recorded at the bottom of the Intervention Session Form. Participants will complete an anonymous session feedback form at the end of each session. Each session will be audio recorded and later transcribed using a third party.

Each session will be reviewed by a member of the research team not participating in the session for fidelity using the fidelity checklist.

Reminder calls

Study staff will conduct up to 5 reminder calls to remind about their upcoming intervention session. Please note the purpose of these calls is to remind about

appointments but in case patient initiates the conversation regarding intervention or other related to the study staff will talk to participant regarding intervention.

If a participant misses a session, they will receive up to 5 reminder calls asking why and what we can do to help. If there are things we can do to help that are reasonable (e.g., more reminders, more transportation assistance, or other things), we will provide them.

If they miss more than one visit, they may receive a call asking about their future participation in the study and whether, if they are unwilling to participate in intervention sessions, they would willing to just complete outcome assessments.

Assessments

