All participants in the intervention group will also receive a baseline, post-intervention (after all sessions are completed), and at about 3 months (1 month leeway) assessment. These may be conducted by phone or in person. They will also participate in an audio-recorded in –person qualitative interview at the mid-point and end of the trial which will be transcribed using a third party company.

Qualitative interviews

Participants assigned to intervention arm, peers and interventionists of the study will be interviewed at mid-point of the study and end of the study to provide their feedback on the STOMP intervention. These interviews will be audio-recorded and later transcribed using third party.

g) CONTROL

The control group will receive “treatment as usual”. The “treatment as usual” or control arm refers to the standard of care that patients receive at the UAB 1917 clinic. This standard of care is for patients to discuss chronic pain with their providers at their

discretion. Although highly variable, providers can recommend and prescribe pharmacologic (e.g., opioid and other pain medication), non-pharmacologic (e.g., physical therapy, referral to psychology) approaches for pain. This study will not interfere in any way with usual care. No additional treatment will be provided to participants allocated to the control group. The control group participants will complete the baseline assessment and around 12 week follow-up (1 month leeway) assessment.

h) SNAP SHOT OF STUDY ACTIVITIES

Procedure	Length of Time Required of Participants	Frequency of Repetition
Individual sessions (intervention group only)	6 sessions, up to approx. 120 minutes each	Maximum of on average every other week
Group sessions (intervention group only)	6 sessions, up to 120 approx minutes each	Maximum of on average every other week
Questionnaire assessments – see attached	Approx 30 minutes	Baseline, end of intervention, and 3 months after intervention
Qualitative interviews (intervention group only)	Approx up to 120 minutes	Midpoint and end of trial
Phone calls (intervention group only)	Approx up to 30 minutes	Average of once weekly

h) SUMMARY OF COMPENSATION

Intervention group

In person for Prescreen	\$25
Screening/Enrolment visit	\$50
Mid-point qualitative interview	\$50
End of study qualitative interview	\$50
Post intervention follow up	\$50
3 month follow up	\$100

Control group

In person for Prescreen	\$25
Screening/Enrolment visit	\$50
12 week assessment	\$50

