3 month follow up	\$100

Offer parking vouchers/coffee vouchers/bus tickets etc. as required to the participants if that is the standard practice followed over at the clinic.

IV. DATA COLLECTION AND MANAGEMENT

All study documentation will be kept in locked file cabinets in BBRB or CCB in study personnel's offices. RedCap database can only be accessed by STOMP personnel using a UAB computer or encrypted laptop.

V. DATA ANALYSIS

Outcomes were reported as means and standard deviations for continuous variables, and frequencies and percentages for categorical variables. T-tests were used to compare change scores for continuous variables and Fisher's exact

tests were used to compare percentages. Interviews were analyzed thematically by two independent coders. Discrepancies were reconciled, a code book was created, and the lead analyst coded the remaining transcripts with continued input from the other coder. Representative quotes are presented for themes that helped us understand why and how the intervention could work.

VI. CRISIS PROTOCOL

As a general note, referrals can be made for crisis consultation at any time. The research staff will document the findings of his/her evaluation and the course of action taken. Providers for the patient may be informed about the same.

VII. PROTECTION OF HUMAN SUBJECTS

Our team has devised a comprehensive plan for ensuring protection of human subjects throughout the course of the proposed study. We will utilize an English-language consent form with common phrasing that describes that no special privileges or considerations will be conferred as a result of study participation, and that access to medical care will not be affected by the potential participant's decision to enroll in the study. The procedures listed in the following sections detail procedures that have been approved and utilized during recent years of clinical and behavioral trials at each site for collaborative research that utilizes sensitive information from participants. Our team will make every effort to protect all participants' confidential and private information in order to minimize possible study-associated risks.

All findings related to this research will be available and provided to study participants in accordance with standard practices. Clinical and measurement data used for research studies will be released only in de-identified fashion.

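### Change-score t-tests use only participants seen at the visit in question and ignore their other follow-up, which costs precision and can bias the preliminary effect if loss relates to response

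*Combined protocol and SAP*

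**What the plan says.** Section II sets the aim as to "investigate feasibility, acceptability, and when possible, preliminary impact". For size, Section III.e says "Approximately, 20 intervention arm and 20 control (standard of care) participants will be randomly assigned".

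Section V holds the whole quantitative plan. For continuous outcomes, "T-tests were used to compare change scores for continuous variables"; percentages go to Fisher's exact test. It does not say which follow-up visit supplies the change score, who is analysed, or what happens when a visit is missing.

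The activity table in Section III.h schedules questionnaires at "Baseline, end of intervention, and 3 months after intervention", without limiting this to one arm. Under Assessments in Section III.f, the intervention arm has a baseline, a "post-intervention (after all sessions are completed), and at about 3 months (1 month leeway) assessment", by phone or in person. Section III.g gives controls a baseline and a single follow-up at around 12 weeks, but the control payment list has both a 12-week assessment and a 3-month follow-up.

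Under Reminder calls in Section III.f, people who miss more than one visit may be called and asked whether, "if they are unwilling to participate in intervention sessions, they would willing to just complete outcome assessments".

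**The concern.** A change score needs both its baseline and its follow-up value. With no imputation rule, a t-test on change at one visit leaves out everyone without that visit, even if they attended the other follow-up. The average effect is then right only if the people left out do not differ in change from those kept, within each arm.

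Loss could well be uneven. Only the intervention arm has 12 sessions to attend, and its post-intervention assessment is placed after all of them. If people who benefit little stop coming, the intervention mean is taken from the better responders and the preliminary effect looks too large. Where only the 3-month visit is missed, the end-of-intervention score that would reveal this has already been collected, but the 3-month test makes no use of it. Adding baseline as a covariate would not settle the matter, because the selection acts on response after baseline.

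At stake is the preliminary effect estimate, together with precision that a trial of about 40 can ill afford to lose.

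**Working it through.** **No figure to reproduce.** The documents give about 20 per arm, 1:1, with baseline and up to two follow-ups. They give no effect size, SD, correlation, dropout rate, alpha or power. Every other input below is an assumption.

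**Inputs, main calculation.** 20 per arm; outcome in SD units, higher meaning better; correlation of baseline with follow-up 0.5; correlation between follow-ups 0.7; true effect 0.40 SD; control loss 20% at random; intervention loss 10% among better and 30-50% among poorer responders at end of intervention. With an even split, overall intervention loss is (10 + 30)/2 = 20% to (10 + 50)/2 = 30%.

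**Estimators of the 3-month effect** (Y0 baseline, Y1 end of intervention, Y2 3 months, A arm):

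- Change-score t-test: mean of Y2 − Y0 among intervention completers, minus the same mean among control completers.
- Completer ANCOVA: the coefficient of A when Y2 is regressed on A and Y0 among those with Y2.
- Model using both follow-ups: regress Y2 on A, Y0 and Y1 among those with Y2 (coefficients b for A, d for Y1). Regress Y1 on A and Y0 among all (coefficient g for A). The estimate is b + d × g.

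**Why baseline adjustment is not enough.** Given Y0, the correlation of Y1 with Y2 is (0.7 − 0.5 × 0.5)/(1 − 0.5²) = 0.45/0.75 = 0.60. Selection on Y1 therefore still shifts Y2 after adjustment for Y0.

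**Average estimates (truth 0.40 SD):**

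| What is missed, and why | Change-score t-test | Completer ANCOVA | Both follow-ups used |
|---|---|---|---|
| 3-month visit only; depends on end-of-intervention change | 0.47-0.56 | 0.44-0.50 | about 0.40 |
| 3-month visit only; depends on end-of-intervention level | 0.42-0.45 | 0.44-0.50 | about 0.40 |
| Both follow-ups, same people; depends on change | 0.47-0.56 | 0.44-0.50 | 0.44-0.50 |

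In relative terms, 0.47/0.40 to 0.56/0.40 is about 18-40% too large, 0.42/0.40 to 0.45/0.40 about 5-12%, and 0.44/0.40 to 0.50/0.40 about 10-25%. If instead the post-intervention visit is missed because of its own unseen value, the model gives 0.45-0.51 at that visit.

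**Second calculation, other assumptions.** Large sample; SD 2; correlations 0.6 (baseline/post), 0.5 (baseline/3-month), 0.7 (post/3-month); lower is better; true effect −1.00; loss of 10/20/30% in the intervention arm only.

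| Reason for loss | t-test | ANCOVA | Both follow-ups used |
|---|---|---|---|
| Unrelated to outcome | about −1.00 | about −1.00 | not run |
| Baseline only (post visit) | −0.93/−0.86/−0.80 | about −1.00 | not run |
| Observed post value; 3-month visit missed | −1.02/−1.03/−1.05 | −1.08/−1.14/−1.21 | −1.00/−1.00/−1.00 |
| Unseen post value; post visit missed, 3-month attended | −1.07/−1.14/−1.20 | −1.12/−1.22/−1.33 | −1.08/−1.16/−1.24 |

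**Precision (main calculation).** The empirical SE is about 0.36-0.37 for the t-test and 0.30-0.31 for the model. When loss is unrelated to outcome it is about 0.345 against 0.295, a variance ratio of (0.345/0.295)² = 1.37. Much of this comes from handling baseline better: residual variance is 2 × (1 − 0.5) = 1.00 for a change score and 1 − 0.5² = 0.75 after adjustment, and 0.345 × √0.75 = 0.30. The other follow-up adds a little more.

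**The case against.** The strongest reply is that the plan already works to keep outcomes apart from session attendance. Those who stop sessions may be offered assessments only, phone assessment is allowed, and the 3-month visit carries the largest payment. This stands as mitigation. It is not a guarantee: the offer is only something participants may receive, and the post-intervention visit is still placed after completion of all sessions. Partial follow-up gained this way also helps only if the analysis uses it.

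A reader might infer that session dropout will bias the result, and upwards. The documents give neither rates nor reasons for loss. Loss unrelated to outcome gives no bias, and loss that depends on baseline pulled the t-test towards zero in the second calculation.

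A reader might also infer that a repeated-measures model cures the problem. It does so only where loss depends on observed data. When the same people miss both follow-ups it does no better than completer ANCOVA, and when the post-intervention visit is missed because of its own value it was slightly worse than the t-test (−1.24 against −1.20 at 30% loss). Nor is ANCOVA always better than the t-test: if loss follows level, its bias is larger.

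Finally, Section V does not announce a complete-case analysis, nor that end-of-intervention data are discarded. The first follows from the method and the absence of any other rule. The second cannot be claimed, since change to that visit may be tested as well.

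Impact is a preliminary aim, and the bias of 0.02-0.16 SD is under half the t-test's SE (0.16/0.37 = 0.43). That lowers the priority, but the precision gain remains.

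**Conclusion.** The point holds in conditional form. As written, Section V uses for each comparison only participants with baseline and that visit, and takes nothing from their other follow-up. This costs precision under the assumed correlations (SE about 0.345 against 0.295) even when loss is harmless. If loss in the intervention arm relates to response, it can also overstate the effect: 0.42-0.56 SD for a true 0.40, depending on whether loss follows level or change. Adjusting completers for baseline does not remove that. Using both follow-ups does when only the 3-month visit is missed for reasons visible at end of intervention, and otherwise may not.

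All sizes rest on assumed correlations, effect and loss rates. The benefit also depends on controls having two follow-ups, on which the documents conflict. The change should be made, but it does not threaten the feasibility and acceptability aims.

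**What to change.** 1. Reconcile the control follow-up: one visit at around 12 weeks in Section III.g, two follow-ups in the Section III.h table and the control payment list. Report between-arm differences only at visits that both arms attend.
2. In Section V, replace the change-score t-tests by one repeated-measures model per continuous outcome. Include all randomised participants in their assigned arm, all available visits, baseline constrained equal across arms, and visit and visit-by-arm effects. Name the covariance structure and a degrees-of-freedom method suited to about 20 per arm.
3. Report the number contributing per arm and visit.
4. Add a short sensitivity analysis for loss that depends on unseen values, for example by shifting the missing intervention-arm outcomes by a range of amounts.

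The cost is a few lines in Section V and slightly more analysis work, with no new data. The model relies on missing-at-random, hence item 4. If controls prove to have a single follow-up, the gain comes mainly from the baseline handling, and little from the second visit.
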